8.3. Data Sources

Data will be collected from the local registry at the Dermatology Center of Baghdad Teaching Hospital. The data are structured and will be analyzed by the investigator.

8.4. Study Size

This study will include approximately 400 patients from the local registry that meet the inclusion criteria detailed in that described previously.

8.5. Data Management

The structured data is exported into an Excel spreadsheet. It will then be transferred to the SPSS database (version 23) which will be used for data management and analysis.

8.6. Data Analysis

Categorical covariances will be described by frequency distribution while continuous covariates will be expressed in terms of their mean and standard deviation or median and interquartile range as appropriate. The unadjusted comparisons between groups of the covariates and the outcomes will be evaluated using chi-squared tests for categorical data, while for continuous data, the student's t-test for normally distributed variables and the Kruskall-Wallis test for non-parametric data will be used.

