5. MILESTONES

Milestone	Planned date
Start of data collection	01 September 2020
End of data collection	01 October 2020
Final study report	01 September 2021

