6. RATIONALE AND BACKGROUND

Iraq has over 5 years of experience in using Enbrel as a treatment for psoriasis patients, starting in 2014 when the first psoriasis patients received the first dose of Enbrel. Dermatologists in Baghdad Teaching Hospital observed a positive response in patients with psoriasis using a biological treatment such as Enbrel, this observation discussed this during our medical to medical interaction. Local data indicates the value of adherence and efficacy to treatment with Enbrel in patients with moderate-to-severe plaque psoriasis after five years of use. This study aims to address the need for evaluating local and regional data of Enbrel use in Iraqi psoriasis patients, as there is no local published and limited regional data, currently. With the expected number of patients for this study, this would be the largest regional study for the evaluation of data on Enbrel use in Iraqi patients with moderate-to-severe psoriasis.

This study will evaluate local data available in Iraqi patients with moderate-to-severe psoriasis on Enbrel treatment with regards to efficacy, treatment-regimen adherence, and patient characterization (ie, age, gender, and smoking status).

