8. RESEARCH METHODS

8.1. Study Design

This is a retrospective analysis of approximately 400 Iraqi patients diagnosed with moderate-to-severe plaque psoriasis that received Enbrel as treatment for disease.

Baseline, 6 months after initiation of Enbrel treatment and last visit follow-up, BSA, PASI, and DLQI scores for identified patients will be collected and used to evaluate efficacy. Patients will be further divided into 2 groups according to their adherence to Enbrel treatment (The adherent group will include the patients who were adherent to Enbrel treatment for one and seven years, and the non-adherent group will include patients who did not adhere to Enbrel). There will then be a comparison between both groups; in BSA, PASI, and DLQI scores at baseline, 6-months after Enbrel treatment, and at last visit follow-up after Enbrel treatment.

Patient demographic information (eg, age gender, disease duration) will be analyzed throughout the study.

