8.2.1. Inclusion Criteria

Patients must meet each of the following inclusion criteria to be eligible for inclusion in the study:

1. Confirmed diagnosis of moderate-to-severe plaque psoriasis and receiving etanercept treatment for a minimum duration of 1 year.
2. Age ≥ 18 years old.
3. No history of using a biological treatment, other than etanercept, for treatment of moderate to severe plaque psoriasis or any other reason.

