9.3. Institutional Review Board (IRB)/Independent Ethics Committee (IEC)

There must be prospective approval of the study protocol, protocol amendments, and other relevant documents (eg, informed consent forms if applicable) from the relevant IRBs/IECs. All correspondence with the IRB/IEC must be retained. Copies of IRB/IEC approvals must be forwarded to Pfizer.

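### Adherent and non-adherent patients are compared on BSA, PASI and DLQI with unadjusted tests only, so any baseline difference between the groups carries into the 6-month and last-visit results

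*Combined protocol and SAP*

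**What the plan says.** Section 8.1 describes a retrospective analysis of about 400 registry patients, divided into an adherent and a non-adherent group. The groups are to be compared "in BSA, PASI, and DLQI scores at baseline, 6-months after Enbrel treatment, and at last visit follow-up after Enbrel treatment".

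Section 8.6 is the only text on analysis. After descriptive summaries it states that "The unadjusted comparisons between groups of the covariates and the outcomes will be evaluated" with chi-squared tests for categorical data and Student's t or Kruskal-Wallis tests for continuous data. No section specifies a regression, ANCOVA, change score, stratification, matching or propensity method.

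Possible adjustment variables are in scope. Section 8.1 says "Patient demographic information (eg, age gender, disease duration) will be analyzed throughout the study", and Section 6 adds smoking status. Neither says how these variables enter the group comparison. Section 8.8 names missing data as the only limitation and does not mention confounding.

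**The concern.** Patients were not assigned to adhere or not. Those who adhere may differ at the outset in disease severity, age, gender, disease duration or smoking. A t-test on the 6-month or last-visit score then mixes that starting difference with whatever goes with adherence. Comparing the groups at baseline can reveal an imbalance, but it does not correct the later comparisons, and a non-significant baseline test does not show balance.

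The last visit has a further problem because it has no fixed time. Eligibility requires "receiving etanercept treatment for a minimum duration of 1 year", so follow-up is at least one year. The upper end is set by first doses "starting in 2014 when the first psoriasis patients received the first dose of Enbrel" and data collection ending on "01 October 2020". The groups may have been followed for different lengths of time at that point; the documents do not say whether they were.

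At stake is any statement the report makes about adherence and response on the three efficacy scores.

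**Working it through.** **Is any adjustment specified?** Section 8.1 sets up the comparison, Section 8.6 limits between-group testing to unadjusted tests, and no other section adds a model. This settles the point without arithmetic. The numbers below only show scale.

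**Inputs**
- N = 400: Sections 8.1 and 8.4, stated as approximate. It comes with no alpha, power, effect size, SD or group split, so there is no plan calculation to reproduce.
- Assumed: no true adherence difference; SD = 1 in both groups; two-sided 5% test; baseline imbalance d = 0.3 SD (range 0.2 to 0.4); baseline-to-follow-up correlation r = 0.5 (range 0.3 to 0.6); several group splits.

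**Formulas**
- Spurious follow-up difference = r × d = 0.5 × 0.3 = 0.15 SD.
- SE = √(1/n₁ + 1/n₂).
- Rejection rate = P(|Z + 0.15/SE| > 1.96).

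**Central case**

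| Split | n₁ / n₂ | SE | 0.15/SE | Rejection rate |
|---|---|---|---|---|
| 50:50 | 200 / 200 | 0.100 | 1.50 | 32.3% |
| 70:30 | 280 / 120 | 0.109 | 1.37 | 28.0% |
| 85:15 | 340 / 60 | 0.140 | 1.07 | 18.8% |
| 95:5 | 380 / 20 | 0.229 | 0.65 | 10.0% |

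The nominal rate is 5%.

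**Range over splits 50:50 to 85:15**
- Lowest: d = 0.2, r = 0.3, 85:15. Difference 0.06 SD, rate 7.1%.
- Highest: d = 0.4, r = 0.6, 50:50. Difference 0.24 SD, rate 67.0%.

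**Effect of adjusting for the baseline score.** Simulation of the central case, 4000 runs per split:

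| Split | t-test | ANCOVA |
|---|---|---|
| 50:50 | 32.7% | 5.3% |
| 70:30 | 28.1% | 4.8% |
| 85:15 | 18.8% | 5.1% |

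Adjustment also multiplies the residual variance by 1 − r² = 1 − 0.25 = 0.75.

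**Follow-up length.** A patient who started at the beginning of 2014 has about 6.75 years to 01 October 2020; one who started at the end of 2014 has about 5.75. The last visit can therefore fall anywhere from 1 year to between 6 and 7 years after the first dose. Section 8.1 mentions adherence of seven years, slightly more than these dates allow. The documents give nothing from which to estimate a difference in follow-up between the groups, so no size is claimed for this part.

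**The case against.** **The comparison is not a listed objective.** Section 7 names the before-after change in scores (primary) and first-year adherence (secondary). This is correct, and neither depends on the group comparison. But Section 8.1 commits to that comparison on all three efficacy scores, so it will be reported and read. This limits the weight of the point without removing it.

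**Section 8.6 openly calls the tests unadjusted, and no causal claim is made.** The label is honest. If it implies that an adjusted analysis was also intended, that analysis is not written down. Naming confounding in Section 8.8 would help, but would still leave the reader without an adjusted estimate.

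**The numbers are assumed.** This stands. Nothing in the documents shows that the groups differ at baseline. The return to about 5% is also partly built in, because the simulated data follow the linear model that ANCOVA fits, with 400 complete cases and no unmeasured confounder. The figures illustrate the mechanism only.

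**Adjustment does not isolate adherence.** This stands too. Adherence is judged over a year or more, so the 6-month score precedes part of what defines the group, and a poor response may itself lead to non-adherence. Unmeasured confounding also remains. The model removes the part due to measured baseline differences and no more.

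**The non-adherent group is poorly defined.** Section 8.1 describes it only as patients who did not adhere, while eligibility requires at least a year of treatment. Its make-up and size are unknown. An operational definition is needed for either analysis, unadjusted or adjusted.

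**Conclusion.** The concern holds. Followed as written, the plan carries any baseline imbalance between the adherence groups into the 6-month and last-visit differences in BSA, PASI and DLQI. At the last visit it may add unequal follow-up as well. A reader could not tell how much of a difference goes with adherence.

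That the plan contains no adjusted analysis is certain from the text. The size is not: it depends on an imbalance, a correlation and a group split that the documents do not give. Moderate assumed values raise the false-positive rate well above nominal. The change should be made, but the listed objectives do not stand or fall with it.

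**What to change.** In Section 8.6, make the main between-group analysis at 6 months and at last visit a linear model (ANCOVA) for each of BSA, PASI and DLQI, and report the adjusted difference with its 95% CI.

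- **Terms:** adherence group, the baseline value of the same score, age, gender, disease duration and smoking status.
- **Skewed scores:** use a transformation or a rank-based version if a score is clearly skewed, and write down the criterion beforehand.
- **Unadjusted tests:** keep them as descriptive.
- **Follow-up length:** if visit dates are in the export, summarise time from first dose to last visit by group and add it to the last-visit model as a sensitivity analysis only. It is a post-baseline variable and may result from non-adherence.
- **Interpretation:** call the result an association, say that response may influence adherence, and add confounding to Section 8.8.
- **Group definition:** state the rule that places a patient in the non-adherent group, and report both group sizes.

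**Cost.** A small amendment to Section 8.6, to which Section 9.3 applies: "There must be prospective approval of the study protocol, protocol amendments, and other relevant documents". The extra SPSS work is slight. The main model uses only variables the protocol names, although no list of export fields confirms that smoking status and disease duration were recorded. Patients missing a baseline score or covariate drop out of a complete-case model, so their number should be reported. Data collection was planned to end in October 2020; if the data have already been seen, the adjusted analysis should be labelled post hoc.

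### Section 8.6 names Student's t-test for two adherence groups that nothing makes equal in size or spread; Welch's test removes the risk to the error rate at almost no cost

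*Combined protocol and SAP*

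**What the plan says.** Section 8.1 forms the groups from what patients did: "Patients will be further divided into 2 groups according to their adherence to Enbrel treatment". It continues: "There will then be a comparison between both groups", namely "in BSA, PASI, and DLQI scores at baseline, 6-months after Enbrel treatment, and at last visit follow-up after Enbrel treatment". Three scores at three time points make nine between-group comparisons.

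Section 8.6 supplies the tests. It begins "The unadjusted comparisons between groups of the covariates and the outcomes will be evaluated using chi-squared tests for categorical data" and adds that for continuous data the "student's t-test for normally distributed variables and the Kruskall-Wallis test for non-parametric data will be used". Descriptive summaries follow the same split: "mean and standard deviation or median and interquartile range as appropriate".

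Section 8.4 gives the total: "This study will include approximately 400 patients from the local registry". The documents do not state the expected split between the groups, any SD, the significance level, the criterion for normality, or whether normality is judged per score, per visit or per group. No unequal-variance form of the t-test is named.

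**The concern.** The plan's only safeguard for the t-test is a judgement about normality. With samples of this size, the assumption more likely to matter is equal variance, because Student's t-test builds its standard error from one pooled variance. When the smaller group is the more variable, the pooled standard error is too small and false positives rise. When the smaller group is the less variable, the standard error is too large and real differences are missed. Adherence decides who falls in which group, without allocation or matching, so equal size and spread cannot be taken for granted.

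A second, lesser issue is interpretation. The t-test compares means and the rank test compares rank order. Because the level at which normality is judged is not stated, one score could be compared on means at baseline and on ranks at 6 months. The results for that score would then not answer the same question across visits.

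**Working it through.** The plan has no figure to reproduce: it states no alpha, power, SD or sample-size derivation. The check is therefore of the mechanism, over a range.

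**Inputs.** From the documents: total of about 400 (Section 8.4), two groups by adherence (Section 8.1), Student's t-test (Section 8.6). Assumed: two-sided alpha 0.05, equal true means, normal data, splits from 200:200 to 360:40, larger group's SD = 1, smaller group's SD = r with r from 0.5 to 2.

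**Formula.** With n1 the larger group and n2 the smaller:

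- True variance of the mean difference: Vtrue = 1/n1 + r²/n2
- Variance used by the test: Vpooled = sp² × (1/n1 + 1/n2), where sp² = [(n1−1) + (n2−1)r²]/(n1+n2−2)
- True type I error ≈ 2 × [1 − Φ(1.966 × √(Vpooled/Vtrue))], where 1.966 is the critical value on 398 degrees of freedom

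**Worked case, 300:100, r = 2.** Vtrue = 1/300 + 4/100 = 0.04333. sp² = (299 + 99×4)/398 = 1.746. Vpooled = 1.746 × (1/300 + 1/100) = 0.02328. √(0.02328/0.04333) = 0.733. 1.966 × 0.733 = 1.441, so the error is 2 × [1 − Φ(1.441)] = 0.150.

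**Opposite direction, 300:100, r = 0.5.** Vtrue = 1/300 + 0.25/100 = 0.00583. sp² = (299 + 99×0.25)/398 = 0.813. Vpooled = 0.01085. The ratio's square root is 1.364, and 1.966 × 1.364 = 2.681, so the error is 0.007.

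**Simulated type I error of the pooled test** (20,000 data sets per cell):

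| Split | r = 0.5 | r = 1.5 | r = 2 |
|---|---|---|---|
| 200:200 | 0.051 | 0.051 | 0.052 |
| 280:120 | 0.012 | 0.093 | 0.125 |
| 300:100 | 0.007 | 0.111 | 0.154 |
| 320:80 | 0.004 | 0.123 | 0.179 |
| 360:40 | 0.001 | 0.154 | 0.242 |

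Formula and simulation agree to within about 0.005. With equal SDs (r = 1) the pooled test gave 0.050 to 0.051 at the four splits simulated (200:200, 280:120, 320:80 and 360:40). Welch's test stayed between about 0.047 and 0.054 throughout.

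**Why a larger N does not help.** In large samples Vpooled/Vtrue tends to (n1 + n2·r²)/(n2 + n1·r²). This depends only on the split and the SD ratio. At 3:1 and r = 2 it is (3+4)/(1+12) = 0.538, whose square root is 0.734, the same inflation as at 300:100.

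**Does the normality step protect?** The rule was simulated with an assumed criterion, Shapiro-Wilk at 0.05 in each group (4,000 runs).

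- Identical distributions in both groups: error 0.046 to 0.052. Choosing by normality does not in itself inflate error.
- Normal data, 320:80, r = 2: error 0.174, against 0.051 for Welch. The normality check does not detect unequal spread.
- Skewed data with equal means and unequal SDs: the rule always chose the rank test, which rejected in 69% of runs (320:80) and 86% (200:200), while Welch stayed at 4.5% to 5.7%. The rank test is not failing here; it is detecting a difference in distribution. The two branches test different hypotheses.

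**The case against.** The strongest reply is that the harm is hypothetical. Section 8.1 does not say that the groups will be unequal, no SD is given, and the pooled test is sound if either sizes or spreads match. Even the direction of any error is unknown. That stands, and it rules out one tempting reading: a reader might infer that the adherence comparison has a demonstrably inflated false-positive rate. The documents do not support that; they only leave the condition unguarded.

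A reader might also infer that the plan orders a fresh normality decision at each visit, or that this decision itself raises the error rate. Section 8.6 refers only to variables and is silent on visits, so mixed comparisons are possible but not stated. In the check above, selection by normality alone held its level.

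It can also be said that pairing means with a t-test and medians with a rank test is conventional and coherent, and that the t-test figures apply only to scores judged normal. Both points are fair. How many of the nine comparisons would reach the t-test is unknown. The rank branch is not a full escape, however: read as a test of equal centres with normal data at 320:80, it rejects in 10.6% of runs when the smaller group has twice the SD and in 1.7% when it has half.

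Finally, Section 8.6 raises larger questions. The comparison is unadjusted and the groups are not randomised, so the exact error rate under equal means is secondary. That supports a low severity. It does not argue for keeping the pooled test.

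**Conclusion.** The point holds as a minor one. Section 8.6 names a test that assumes equal variances for groups whose size and spread nothing in the design equalises. Under the assumptions of two-sided alpha 0.05, 400 patients and normal data, true type I error at 300:100 to 320:80 is about 10-12% when the smaller group's SD is 1.5 times the larger group's, 15-18% when it is twice, and below 1% when it is half. It is nominal when sizes or SDs are equal. Because sizes, SDs and alpha are absent from the documents, these figures show what could happen and are not evidence of an error in the study's results. The possible mixing of means and ranks for one score is a matter of interpretability only.

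**What to change.** In Section 8.6, replace Student's t-test with Welch's unequal-variance t-test, and report the mean difference with its 95% confidence interval for BSA, PASI and DLQI at baseline, 6 months and last visit. State that a given score is analysed by the same method at all visits. Report the rank test alongside as a sensitivity analysis, read as a comparison of distributions and not of means. For markedly skewed scores, also describe medians and interquartile ranges, so that the summary and the test can be read together. Making means primary for such scores is a judgement on which statisticians may differ; replacing the pooled variance does not depend on it.

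The statistical cost is small: at most about 1.5 percentage points of power if the variances are in fact equal. No new data are needed. The change is a few sentences, although Section 9.3 requires ethics committee approval of protocol amendments. Section 5 places the end of data collection at 01 October 2020, so if the analysis has already been run, the Welch results should be added to the report and labelled as such. None of this addresses confounding in the unadjusted comparison.

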8.7. Quality Control

Not applicable.

8.8. Limitations of the Research Methods

Missing data that could lead to bias is an identified limitation in this study.

8.9. Other Aspects

Not applicable.

9. PROTECTION OF HUMAN SUBJECTS

9.1. Patient Information

This study involves data that exist in anonymized structured format and contain no patient personal information.

9.2. Patient Consent

As this study involves anonymized structured data, which according to applicable legal requirements do not contain data subject to privacy laws, obtaining informed consent from patients by Pfizer is not required.

9.3. Institutional Review Board (IRB)/Independent Ethics Committee (IEC)

There must be prospective approval of the study protocol, protocol amendments, and other relevant documents (eg, informed consent forms if applicable) from the relevant IRBs/IECs. All correspondence with the IRB/IEC must be retained. Copies of IRB/IEC approvals must be forwarded to Pfizer.

9.4. Ethical Conduct of the Study

The study conducted in accordance with legal and regulatory requirements, as well as, with scientific purpose, value, and rigor and follow generally accepted research practices described in Guidelines for Good Pharmacoepidemiology Practices (GPP) issued by the International Society for Pharmacoepidemiology (ISPE), Good Epidemiological Practice (GEP) guidelines issued by the International Epidemiological Association (IEA), and Good Practices for Outcomes Research issued by the International Society for Pharmacoeconomics and Outcomes Research (ISPOR).

10. MANAGEMENT AND REPORTING OF ADVERSE EVENTS/ADVERSE REACTIONS

This study involves data that exist as structured data by the time of study start.

In these data sources, individual patient data are not retrieved or validated, and it is not possible to link (ie, identify a potential association between) a particular product and medical event for any individual. Thus, the *minimum criteria for reporting an adverse event (AE) (ie, identifiable patient, identifiable reporter, a suspect product, and event) cannot be met.*

11. PLANS FOR DISSEMINATING AND COMMUNICATING STUDY RESULTS

In the event of any prohibition or restriction imposed (eg, clinical hold) by any applicable competent authority in any area of the world, or if the investigator is aware of any new information that might influence the evaluation of the benefits and risks of a Pfizer product, Pfizer should be informed immediately.

13. LIST OF TABLES

Not applicable.

[figure not shown]
